6.2 DETAILS OF TRIAL PROCEDURES AT SELECTED VISITS

6.2.1 Screening and run-in period

Informed consent visit (Visit 0)

- Informed consent will be obtained prior to patient participation in the trial, which includes any medication washout procedures or restrictions. Upon obtaining informed consent, the patient will be instructed on the medication washout and other restrictions

for the screening pulmonary function test at Visit 1.

- Patients taking LAMA should discontinue the treatment more than 3 weeks prior to Visit 2. Alternative bronchodilator medications may be introduced at the investigator's discretion (See [Section 4.2.2](#)).
- The patient will receive directions on the as needed use of the salbutamol MDI (as rescue medication) that will be dispensed at this visit.
- A preliminary check of in-/exclusion criteria is recommended at Visit 0 to avoid unnecessary washout procedures in non-eligible patients.
- Upon obtaining Informed Consent, the patient will receive a trial identification card and a patient appointment card (visit schedule), templates will be provided by the sponsor.

Observations and procedures at Visit 1

- Visit 1 will be scheduled within 28 days after signing informed consent (the period of time between signing informed consent and Visit 1 will depend on medication washout requirements).
 - Blood samples will be collected for haematology, serum chemistry and pregnancy testing (if applicable). Blood samples need to be taken prior to the salbutamol dosing.
 - Pulmonary function testing with the CHEST spirometer will be conducted between 7:00 AM and 10:00 AM, 10 min prior to the inhalation and between 10 to 15 min after the inhalation of 4 puffs of salbutamol, (reversibility testing).
 - Patients qualified to enter the 2-week (up to 4-week) screening period of the trial will be issued additional rescue medication, if needed.
 - Patients will receive training and instructions on
 - the use of the RESPIMAT inhaler in using the training RESPIMAT inhaler containing placebo
 - the use of rescue medication (salbutamol MDI)
 - medication restrictions (i.e. washout of LAMA) for the screening period and subsequent visits
 - returning all issued medication and the patient medication work sheet to the site on all subsequent visits.

Screening Period

If there is any indication during the screening period that the patient is not stable enough to complete the trial or that the patient will be non-compliant with the trial medication or restrictions, the patient should not be treated. This evaluation should take place by the

investigator.

Details of any patient who is screened for the trial but is found to be ineligible must be entered in the Enrolment Log and documented in the eCRF.

6.2.2 Treatment periods

6.2.2.1 Visit 2

- 12-lead ECG will be measured before test drug administration..
- Trial medications must be administered in an area isolated from PK sampling and from other patients' administration in order to prevent any environmental contamination.
- Urine pregnancy test and laboratory test sampling should be done before dispensing urine for blank PK samples.
- The patient should be instructed to empty the bladder prior to dosing. .
- Urine sampling for PK measurement: Post-dosing urine sampling will be performed as indicated in the "[Timing of procedure at Visit 2](#)".
- Blood sampling for PK measurement: Blood sampling will be performed 5min (\pm 5 min) before the trial drug administration and post-dose at indicated in the "Timing of procedure at Visit 2".
- Before dosing with trial medication, site personnel should ensure that the patient knows how to use and inhale properly from the RESPIMAT inhaler. A training inhalation with placebo will be performed as indicated in the "Timing of procedure at Visit 2"
- The patient will be issued a patient medication worksheet to record their trial medication use, the time of administration of trial medication as of 3 days before Visit 3 and other concomitant therapy used between Visit 2 and 4 date. Patients will be instructed to return to the site with the medication worksheet at the Visit 4, so that the medication worksheet can be collected and reviewed.

6.2.2.2 Visit 3

- Trial medications must be administered in an area isolated from PK sampling and from other patients' administration in order to prevent any environmental contamination.

- Blood sampling for PK measurement: Blood sampling will be performed 15 min prior to trial medication administration and post-dose at indicated in the “Timing of procedure at Visit 3”
- Three days prior to the clinic visits on days 7, 14 and 18, a telephone contact will be made to each patient in order to remind him/ her of the medication restrictions, the use of the medication worksheet and to bring their trial medication to the site at Visit 3. From day 18 up to the end of Visit 4, the patient will stay in the clinic.

6.2.2.3 Visit 4

- Drug administration time should be within ± 5 min of the time of drug inhalation at Visit 2.
- Trial medications must be administered in an area isolated from PK sampling and from other patients’ administration in order to prevent any environmental contamination.
- Urine pregnancy test and laboratory test sampling should be done before inhalation of trial medication.
- Urine sampling for PK measurement: The patient should be asked to empty the bladder prior to dosing. Post-dosing urine sampling will be performed as indicated in the “[Timing of procedure at Visit 4](#)”.
- Blood sampling for PK measurement: Blood sampling will be performed 15 min prior to trial medication administration and post-dose as indicated in the “Timing of procedure at Visit 4”.
- 12-lead ECG will be measured after last PK sampling.

Note:

If the patient did not take one of the trial medication for the 3 days preceding day 18, this visit must be re-scheduled after at least 10 days continual administration.

6.2.3 Follow Up Period and Trial Completion

Following the treatment phase of the trial, i.e. following the end of 3-week treatment period, patients will be followed up for an additional 3 weeks period. Patients may return to their regular medication after completion of Visit 4. They will be seen at the end of this period (Visit 5) and their AEs, concomitant therapies will be reviewed and recorded. A urine

pregnancy test will be performed where applicable. Dispensed rescue medication (as needed) must be returned. If the physical examination, vital signs or laboratory tests performed at Visit 4 yield abnormal values representing clinically significant changes from baseline, they (for 12-lead ECG) will be repeated at the follow-up visit (Visit 5). Any persistently abnormal test must be fully explained by the investigator and follow-up evaluation performed, if necessary. Additionally, all (S)AEs that occur within 21 days after a patient terminates trial medication must be reported.

The sponsor must be consulted on all persistently abnormal tests and (S)AEs until it is agreed that follow-up is no longer necessary.

6.2.4 Premature withdrawal

The physical examination (including vital signs), clinical laboratory test, PK sampling and one 12-lead ECG will be performed following any premature withdrawal in a withdrawal visit at the earliest convenience. For patients who discontinue early, whether PK sampling will be obtained or not will be determined by discussion between investigator and TCM. Any AEs and changes in concomitant therapies will be recorded. The current patient medication worksheet is to be collected. Patients should be converted to their regular medication upon premature withdrawal. The investigator should make every effort to perform a follow-up visit; 3 weeks after the withdrawal visit (please see [flow chart](#)). During follow-up period, rescue medication is dispensed as needed. If the physical examination, vital signs, 12-lead ECG, or laboratory tests performed at the withdrawal visit yield abnormal values representing clinically significant changes from baseline, they will be repeated at the follow-up visit (Visit 5).

The sponsor must be consulted on all persistently abnormal tests and (S)AEs until it is agreed that follow-up is no longer necessary.

7. STATISTICAL METHODS AND DETERMINATION OF SAMPLE SIZE

7.1 STATISTICAL DESIGN - MODEL

Design

This is an open-label trial in which 3 weeks of treatment are preceded by a 2-week screening period and followed by a 3-week follow-up period.

Objectives

The objectives of this trial is to assess the pharmacokinetics and safety of tiotropium + olodaterol FDC (5 µg/5 µg) delivered by the RESPIMAT inhaler after single dose and at steady state in Chinese patients with COPD.

Endpoints

No efficacy endpoint is defined in this trial. For safety and pharmacokinetic endpoints, see [Sections 5.3](#) and [5.4.1](#), respectively.

Baseline

In general, baseline value will be defined as the last measurement before the first trial drug intake at Visit 2.

7.2 NULL AND ALTERNATIVE HYPOTHESES

No efficacy endpoint is defined in the trial. It is not planned to test any statistical hypothesis with regard to pharmacokinetic and safety endpoints.

[figure not shown]
7.3 PLANNED ANALYSES

7.3.1 Primary endpoint analyses

See [Sections 7.3.5](#) for pharmacokinetic analyses which are the primary objectives of this trial.

7.3.2 Secondary endpoint analyses

See [Sections 7.3.4](#) for safety analyses which are the secondary objectives of this trial.

7.3.4 Safety analyses

Adverse events will be coded using the Medical Dictionary for Regulatory Activities (MedDRA) coding dictionary. Standard BI summary tables and listings will be produced. All adverse events with an onset between start of treatment and end of the residual effect period (REP), a period of 21 days after the last dose of trial medication, will be assigned to the treatment period for evaluation.

All treated patients will be included in the safety analysis. In general, safety analyses will be descriptive in nature and will be based on BI standards. No hypothesis testing is planned.

Statistical analysis and reporting of adverse events will concentrate on treatment-emergent adverse events. To this end, all adverse events occurring between start of treatment and end of the residual effect period will be considered 'treatment-emergent'. Adverse events that start before first drug intake and deteriorate under treatment will also be considered as 'treatment-emergent'.

Frequency, severity, and causal relationship of adverse events will be tabulated by system organ class and preferred term after coding according to the current version of the Medical Dictionary for Drug Regulatory Activities (MedDRA).

Laboratory data will be analysed both quantitatively as well as qualitatively. The latter will be done via comparison of laboratory data to their reference ranges. Values outside the reference range as well as values defined as clinically relevant will be highlighted in the listings.

Vital signs, physical examinations, or other safety-relevant data observed at screening, baseline, during the course of the trial and at the end-of-trial evaluation will be assessed with regard to possible changes compared to findings before start of treatment.

7.3.5 Pharmacokinetic analyses

Concentrations will be used for graphs and calculations in the format that is reported in the bioanalytical report. Only concentrations within the validated concentration range will be used for the calculation of PK parameters.

Plasma concentrations will be plotted graphically versus time for all subjects as listed in the

drug plasma concentration-time tables. For the presentation of the mean profiles the arithmetic mean and the planned blood sampling times will be used.

The following descriptive statistics will be calculated for plasma concentrations as well as for all PK parameters: N, arithmetic mean, standard deviation, minimum, median, maximum, arithmetic coefficient of variation, geometric mean, and geometric coefficient of variation. The descriptive statistics of PK parameters will be calculated using the individual values with the number of decimal places as provided by the evaluation program. Then the individual values as well as the descriptive statistics will be reported with three significant digits in the CTR.

Time to attainment of steady-state will be explored by repeated-measurement ANOVA model through pairwise comparing trough concentrations and concentrations at 20 min after drug administration on days 1, 7, 14, 18-21. The model will be on logarithm scale including “subject” as a fixed effect and “time” as a repeated effect.

7.4 INTERIM ANALYSES

No interim analyse is planned.

7.5 HANDLING OF MISSING DATA

7.5.1 Plasma concentration - time profiles

Concentration data identified with NOS (no sample), NOR (no valid result), NOA (not analysed), BLQ (below the limit of quantification) will be ignored and not replaced by zero at any time point (applies also to the lag phase including the pre-dose value). Descriptive statistics of concentrations at specific time points will be calculated only when at least 2/3 of the individuals have concentrations within the validated concentration range. The overall sample size to decide whether the “2/3 rule” is fulfilled will be based on the total number of samples intended to be drawn for that time point (i.e. BLQ, NOR, NOS, NOA are included). Every effort will be made to include all concentration data in an analysis. If not possible a case by case decision is required whether the value should only be excluded from half-life estimation or the complete analysis.

- If a concentration is only excluded from half life determination, it will be used for all other calculations (e.g. descriptive statistics) and for graphical presentation.

- If a concentration value is excluded from all calculations, it will not be presented graphically or used for the calculation of descriptive statistics and parameter determination. However, the excluded concentration itself will be listed in the tables in the CTR associated with an appropriate flag.

7.5.2 Pharmacokinetic parameters

In the non-compartmental analysis concentration data identified with NOS, NOR, and NOA will not be considered. BLQ values in the lag-phase will be set to zero. The lag phase is defined as the period between time zero and the first time point with a concentration above the quantification limit. All other BLQ values of the profile will be ignored.

Descriptive statistics of parameters are calculated only when at least 2/3 of the individual parameter estimates of a certain parameter are available. If the actual sampling time will not be recorded or will be missing for a certain time point, the planned time will generally be used for this time point instead. Pharmacokinetic parameters which cannot be determined will be identified by "not calculated" (NC).

7.5.3 Safety

It is not planned to impute missing values for safety data, except for missing or incomplete AE dates. Missing or incomplete AE dates will be imputed according to BI standards.

7.6 RANDOMISATION

Not applicable

7.7 DETERMINATION OF SAMPLE SIZE

The sample size is not determined based on formal calculation since this is a study for assessing PK and safety. The size of 12 patients is commonly used in multiple dose Phase I trial of this type. Assuming a dropout rate of 25%, 4 more patients will be needed. Thus, at least 16 patients are planned to be entered into the trial. Should the drop-out rate raise over 25%, additional patients will be entered to reach the target of 12 evaluable patients.

8. INFORMED CONSENT, DATA PROTECTION, TRIAL RECORDS

The trial will be carried out in compliance with the protocol, the ethical principles laid down in the Declaration of Helsinki, in accordance with the ICH Harmonized Tripartite Guideline for Good Clinical Practice (GCP), relevant BI Standard Operating Procedures (SOPs), and relevant regulations*.

The investigator should inform the sponsor immediately of any urgent safety measures taken to protect the study subjects against any immediate hazard, and also of any serious breaches of the protocol/ICH GCP.

The rights of the investigator/ trial site and of the sponsor with regard to publication of the results of this trial are described in the investigator contract/trial site's contract. As a general rule, no trial results should be published prior to finalisation of the CTR.

The certificate of insurance cover is made available to the Investigator and the patients, and is stored in the ISF (Investigator Site File)."

8.1 TRIAL APPROVAL, PATIENT INFORMATION, AND INFORMED CONSENT

This trial will be initiated only after all required legal documentation has been reviewed and approved by the respective Institutional Review Board (IRB) / Independent Ethics Committee (IEC) and competent authority (CA) according to national and international regulations. The same applies for the implementation of changes introduced by amendments.

Prior to patient participation in the trial, written informed consent must be obtained from each patient (or the patient's legally accepted representative) according to ICH / GCP and to the regulatory and legal requirements of the participating country. Each signature must be personally dated by each signatory and the informed consent and any additional patient-information form retained by the Investigator as part of the trial records. A signed copy of the informed consent and any additional patient information must be given to each patient or the patient's legally accepted representative."

The Investigator must give a full explanation to trial patients including the items listed below in association with the use of the patient information form, which is prepared avoiding the use of technical terms and expressions. The patient is given sufficient time to consider participation in the trial. The Investigator obtains written consent of the patient's own free will with the informed consent form after confirming that the patient understands the contents.

The Investigator must sign (or place a seal on) and date the informed consent form. If a trial collaborator has given a supplementary explanation, the trial collaborator also signs (or places a seal on) and dates the informed consent.

Re-consenting may become necessary when new relevant information becomes available and should be conducted according to the sponsor's instructions.

8.2 DATA QUALITY ASSURANCE

This trial will be conducted in accordance with the ICH-GCP guidelines, local regulations and BI SOPs.

In order to achieve a high level of standardised processes, data collection of PK will be coordinated centrally.

A laboratory at site will be used to collect, analyse and report the results of all blood samples and cultures. The site laboratory need to be certified.

Training will be provided to all investigators, coordinators and CRAs to ensure consistency and accuracy of the data. The data will be source verified by the CRAs.

The data management procedures to ensure the quality of the data are described in detail in the trial data management and analysis plan (TDMAP) available in the TMF.

A quality assurance audit/inspection of this trial may be conducted by the Sponsor, Sponsor's designees, or by IRB / IEC or by regulatory authorities. The quality assurance auditor will have access to all medical records, the Investigator's trial-related files and correspondence, and the informed consent documentation of this clinical trial.

8.3 RECORDS

Case Report Forms (e)CRF for individual patients will be provided by the Sponsor. See [Section 4.1.5.2](#) for rules about emergency code breaks. For drug accountability, refer to [Section 4.1.8](#).

8.3.1 Source documents

Source documents provide evidence for the existence of the patient and substantiate the integrity of the data collected. Source documents are filed at the Investigator's site.

Data reported on the CRF must be consistent with the source data or the discrepancies must be explained. The Investigator may need to request previous medical records or transfer records, depending on the trial; current medical records must also be available.

For eCRFs all data must be derived from source documents.

8.3.2 Direct access to source data and documents

The Investigator / institution will permit trial-related monitoring, audits, IRB / IEC review and regulatory inspection, providing direct access to all related source data / documents. eCRF and all source documents, including progress notes and copies of laboratory and medical test results must be available at all times for review by the Sponsor's clinical trial monitor, auditor and inspection by health authorities (e.g. FDA). The Clinical Research Associate (CRA) / on site monitor and auditor may review all eCRF, and written informed consents. The accuracy of the data will be verified by reviewing the documents described in [section 8.3.1](#).

8.3.3 Storage period of records

Trial site:

The trial site must retain the source documents and essential documents for a period defined by the GCP regulation and trial site's contract with the sponsor.

Sponsor:

The Sponsor must retain the essential documents according to the Sponsor's SOPs.

8.4 LISTEDNESS AND EXPEDITED REPORTING OF ADVERSE EVENTS

8.4.1 Listedness

To fulfil the regulatory requirements for expedited safety reporting, the Sponsor evaluates whether a particular adverse event is "listed", i.e. is a known side effect of the drug or not. Therefore, a unique reference document for the evaluation of listedness needs to be provided. For the 5 µg tiotropium inhalation solution this is the current version of the Investigator's Brochure [[U06-3029](#)]. For the 5 µg olodaterol inhalation solution this is the current version of the Investigator's Brochure [U06-3029]. For the FDC of tiotropium and olodaterol this is the current version of the Investigator's Brochure [U06-3029]. For the non-investigational medicinal product salbutamol the reference document is the US-PI (Proair HFA) and for the non-investigational medicinal product ipratropium bromide, the reference document is the UK-SPC (Atrovent Inhaler CFC-Free). The current versions of these reference documents

are to be provided in the ISF. No AEs are classified as listed for matching placebo (for training purposes only), study design, or invasive procedures.

8.4.2 Expedited reporting to health authorities and IEC / IRB

Expedited reporting of serious adverse events, e.g. suspected unexpected serious adverse reactions (SUSAR) to health authorities and IEC / IRB, will be done according to local regulatory requirements.

8.6 END OF TRIAL

The end of the trial is defined as all subjects finished visit 5 or follow the agreement between sponsor and investigator.

8.7 PROTOCOL VIOLATIONS

The investigator should document any deviation from the protocol regardless of their reasons. Only when the protocol was not followed in order to avoid an immediate hazard to trial subjects or for other medically compelling reason, the principal investigator should prepare and submit the records explaining the reasons thereof to the sponsor, and retain a copy of the records.

8.8 COMPENSATION AVAILABLE TO THE PATIENT IN THE EVENT OF TRIAL RELATED INJURY

In the event of health injury associated with this trial, the Sponsor is responsible for compensation based on the contract signed by the trial site.

10. APPENDICES

10.1 PHARMACOKINETIC METHODS

Concentrations will be used for calculations in the format that is reported in the bioanalytical report. The data format for descriptive statistics of concentrations will be identical with the data format of the respective concentrations. For the calculation of PK parameters, only concentrations within the validated concentration range will be used. The descriptive statistics of PK parameters will be calculated using the individual values with the number of decimal places as provided by the evaluation program. Then the individual values as well as the descriptive statistics will be reported with three significant digits in the CTR. The actual sampling times will be used. For pre-dose samples, the actual sampling time will be set to zero. Noncompartmental PK parameters will be determined using WinNonlin or another validated program.

Analyte plasma concentrations will be plotted graphically versus time for all subjects as listed in the analyte plasma concentration-time tables. For the presentation of the mean profiles, the arithmetic mean and the planned blood sampling times will be used.

Individual $C_{\max(ss)}$ and $t_{\max(ss)}$ values will be directly determined from the plasma concentration time profiles of each subject. If the same $C_{\max(ss)}$ concentration occurs at different time points, $t_{\max(ss)}$ is assigned to the first occurrence of $C_{\max(ss)}$.

AUC: The area under the curve will be calculated using the linear up/log down algorithm. If an analyte concentration is equal to or higher than the preceding concentration, the linear trapezoidal method will be used. If the analyte concentration is smaller than the preceding concentration, the logarithmic method will be used.

Linear trapezoidal rule ($t_2 > t_1$ and $C_{t_2} \geq C_{t_1}$):

The area of the trapezoid between the two data points (t_1, C_{t_1}) and (t_2, C_{t_2}) will be computed by:

$$AUC_{t_1-t_2} = 0.5 \times (t_2 - t_1) \times (C_{t_1} + C_{t_2})$$

Logarithmic trapezoid rule ($t_2 > t_1$ and $C_{t_2} < C_{t_1}$):

The area of the trapezoid between the two data points (t_1, C_{t_1}) and (t_2, C_{t_2}) will be computed by:

$$AUC_{t_1-t_2} = \frac{(t_2 - t_1) \times (C_{t_2} - C_{t_1})}{\ln(C_{t_2}/C_{t_1})}$$

$MRT_{ih,ss}$: $MRT_{ih,ss}$ calculation in the steady state will be performed according to the

following equation:

$$MRT_{ih,ss} = \frac{AUMC_{ss}}{AUC_{r,ss}}$$

AUMC_{ss} is the area under the first moment curve at steady state.

[REDACTED]

R_{A,Cmax} and R_{A,AUC}: Accumulation ratios are derived as follows for the respective doses:

$$R_{A,Cmax} = \frac{C_{max,ss}}{C_{max}}$$

$$R_{A,AUC} = \frac{AUC_{t1-t2,ss}}{AUC_{t1-t2}}$$

gMean, gCV: The geometric mean (gMean) and coefficient of variation, gCV (given in %), will be calculated by the formulae:

$$gMean = \exp \left[\frac{1}{n} \sum_{i=1}^n \ln(x_i) \right] = \exp \left[\overline{\ln(x_i)} \right]$$

$$gCV(\%) = 100 \cdot \sqrt{\exp[\text{Var}(\ln(\bar{x}))] - 1}$$

where

$$\text{Var}(\ln(x_i)) = \frac{1}{n-1} \sum_{i=1}^n \left[\ln(x_i) - \overline{\ln(x_i)} \right]^2$$

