5.4 DRUG CONCENTRATION MEASUREMENTS AND PHARMACOKINETICS

5.4.1 Assessment of Pharmacokinetics

As far as feasible, the following pharmacokinetic parameters will be determined for tiotropium and olodaterol, after a single dose at Visit 2 (day 1) and after multiple dosing at

Visit 4 (3 weeks after 1st drug administration). Single dose:

- C_{\max} (maximum measured concentration in plasma).
- t_{\max} (time from dosing to the maximum concentration in plasma).
- $AUC_{t_1-t_2}$ (area under the concentration time curve in plasma over the time interval t_1 to t_2).

[REDACTED]

Multiple dosing

(If steady state can be reasonably assumed, the parameters will be denoted with 'ss' as shown; otherwise, they will be denoted with the dose number of the last dose):

- $C_{\max,ss}$ (maximum measured concentration in plasma at steady state).
- $t_{\max,ss}$ (time from dosing to the maximum concentration in plasma at steady state).
- $AUC_{t_1-t_2,ss}$ (area under the concentration time curve in plasma over the time interval t_1 to t_2 at steady state).

[REDACTED]

- $AUC_{\tau,ss}$ (area under the concentration-time curve in plasma at steady state over a uniform dosing interval τ at steady state).
- $MRT_{ih,ss}$ (mean residence time in the body after inhalation at steady state)
- $C_{pre,ss}$ (pre-dose concentration in plasma at steady state).

[REDACTED]

[REDACTED]

[REDACTED]

In addition, accumulation ratios in plasma ($R_{A,C_{\max}}$ and $R_{A,AUC}$) will be calculated based on $C_{\max,ss}/C_{\max}$ and $AUC_{t_1-t_2,ss}/AUC_{t_1-t_2}$, respectively.

Further pharmacokinetic parameters may be calculated as appropriate. Terminal half-lives and terminal rate constants in plasma at steady state ($t_{1/2,ss}$, $\lambda_{z,ss}$) will be calculated if sufficient data points from the terminal phase are available, i.e. plasma concentrations are quantifiable up to the 24-hour post dose sampling time point.

For investigation of the attainment of steady state, the plasma concentrations prior to dosing and 20 min after dosing will be determined on days 7, 14, 18, 19, and 20 on visit 3.

See [Appendix 10.1](#) for details derivation of pharmacokinetic parameters.

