#### Pharmacokinetic:

The derivation of standard pharmacokinetic parameters will be performed according to 001-MCS-36-472 [\(1\)](#).

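### Does the MRT_ih,ss equation in Protocol Appendix 10.1 give a wrong mean residence time because AUMC_ss has no integration limits?

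*Protocol*

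**What the plan says.** Protocol Section 5.4.1 lists MRT_ih,ss, the "mean residence time in the body after inhalation at steady state", among the multiple-dose parameters to be determined as far as feasible for tiotropium and olodaterol. It refers to Appendix 10.1 "for details derivation of pharmacokinetic parameters".

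Appendix 10.1 states that the MRT_ih,ss "calculation in the steady state will be performed according to the" equation shown there: AUMC_ss over the one-interval steady-state AUC. The subscript is read here as tau, which matches AUC_tau,ss in Section 5.4.1. The only visible explanation of the numerator is that "AUMC_{ss} is the area under the first moment curve at steady state". A redacted block follows.

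Three other provisions bear on the calculation:

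- **Software.** Appendix 10.1 says "Noncompartmental PK parameters will be determined using WinNonlin or another validated program".
- **Sponsor standard.** SAP Section 5.4 says "The derivation of standard pharmacokinetic parameters will be performed according to 001-MCS-36-472". SAP Section 7.9 adds a related reference document and CTP Section 7.3.
- **Missing values.** Section 5.4.1 allows a terminal half-life and rate constant only if enough terminal-phase points exist, that is, if "plasma concentrations are quantifiable up to the 24-hour post dose sampling time point". Section 7.5.2 says "Pharmacokinetic parameters which cannot be determined will be identified by" the code NC, and allows a summary only when at least 2/3 of the individual estimates exist.

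**The concern.** The denominator covers one dosing interval of 24 h, and the numerator has no stated limits. There are two plain readings of the symbol, and neither gives a mean residence time.

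With AUMC taken over 0 to tau, the ratio is a concentration-weighted average time within the dosing interval. It cannot exceed 24 h, however long the drug stays in the body. With AUMC taken over 0 to infinity, drug left from earlier doses enters the numerator but is set against one interval's AUC, so accumulation inflates the result.

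Protocol Section 3.2 cites a half-life of about 60 h for both compounds, long against a 24 h interval, and the two readings then differ widely. If either were applied literally, the clinical trial report would carry a mean residence time that is far too low or far too high.

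**Working it through.** The documents state no MRT value, so there is no figure to reproduce. The check asks which numerator makes the printed ratio correct, and how far the other readings would miss.

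**Inputs**

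- tau = 24 h (once-daily dosing, Protocol Section 4.1.1).
- Terminal half-life of about 60 h (Protocol Section 3.2). Its source, listed in Section 9.2, is a 14-day trial in healthy male volunteers at other dose combinations, so it serves only as an illustration.
- Steady-state profile sampled for 24 h after the dose at Visit 4 (Protocol Section 3.1).
- Assumptions: linear kinetics at steady state and, for the numbers, mono-exponential decline.

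**Which numerator is right**

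Let C(t) be the single-dose curve. At steady state C_ss(t) = Σ C(t + n·tau), summed over n = 0, 1, 2, …

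1. Integrating over one interval gives AUC_tau,ss = AUC_0-inf of a single dose. The printed denominator is therefore the right one.
2. The single-dose first moment splits by interval: AUMC_0-inf = Σ ∫₀^tau (t + n·tau)·C(t + n·tau) dt = AUMC_0-tau,ss + tau × Σ n·∫₀^tau C(t + n·tau) dt.
3. The last sum equals AUC_tau-inf,ss, the area beyond tau if no further dose is given.

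Hence MRT = [AUMC_0-tau,ss + tau × AUC_tau-inf,ss] / AUC_tau,ss. This needs linearity but no compartment model.

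**Numbers at a 60 h half-life**

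k = ln 2 / 60 = 0.01155 per h; r = exp(−24k) = 0.7579; 1 − r = 0.2421.

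| Quantity | Formula | Result |
|---|---|---|
| Mean residence time | 1/k | 86.56 h |
| Ratio with AUMC over 0 to tau | 1/k − 24r/(1 − r) | 86.56 − 75.12 ≈ 11.45 h (13%) |
| Ratio with AUMC over 0 to infinity | 1/[k(1 − r)] | 357.5 h (4.13 times) |
| Tail term, tau × AUC_tau-inf,ss / AUC_tau,ss | 24r/(1 − r) | 75.12 h |
| Ratio with the composite numerator | 11.45 + 75.12 | 86.56 h, allowing for rounding |

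**Dependence on half-life**

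At a 5 h half-life the mean residence time is 7.21 h, and the two plain readings give 6.32 h and 7.48 h. The discrepancy matters only when the half-life is long against 24 h.

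**What the composite numerator rests on**

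At 60 h the tail term is 75.12 / 86.56 = 87% of the result, and it is extrapolated as C24/lambda_z. Concentration falls by only 1 − 0.7579 = 24% over the sampled 24 h. An assumed slope error of +20% gives 11.45 + 75.12/1.2 = 74.0 h; an error of −20% gives 11.45 + 75.12/0.8 = 105.3 h.

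**The case for a change.** The strongest case for a change is that the protocol presents this equation as the rule. Section 5.4.1 sends the reader to Appendix 10.1, and the appendix says the calculation follows the equation. The same appendix gives t1–t2 limits for its AUC rules and for the AUC accumulation ratio, but none here. The PK text under CTP Section 7.3, to which SAP Section 7.9 points, has no MRT formula. The choice of program is left open. The sentence defining AUMC_ss is complete before the redaction begins, so the hidden block may concern another parameter. Section 7.3.5 plans descriptive statistics for all PK parameters, so MRT_ih,ss would be reported for both compounds. Stating the numerator would take one line.

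The visible definition is indeed incomplete, and the algebra is sound. What does not follow is that a wrong value will be calculated. The one-interval AUC is the correct steady-state denominator, and the named quantity is residence time in the body. Together these point to the composite numerator, the only one of the three that makes the equation true. The redacted block, the sponsor standard and the program cannot be read, so their content cannot be counted as absent. The 0 to infinity reading is the less natural one, since it sets an unlimited numerator over a one-interval denominator when sampling stops at 24 h.

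**Conclusion.** No change to the plan follows. Appendix 10.1 uses a symbol without visible limits in an equation that is correct once the symbol has its proper steady-state meaning. A PK analyst working to the cited sponsor standard with a validated program can be expected to use that meaning; the visible documents neither confirm nor contradict this.

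The gaps of 86.6 h against 11.4 h or 357 h show what a literal misreading would cost under linear, mono-exponential kinetics with a 60 h half-life. They are not an expected error for this trial: the half-life comes from healthy men at other dose combinations, and at 5 h the readings nearly agree.

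The consequence is small in any case. MRT_ih,ss is not among the primary endpoints (Protocol Section 5.1.1) or the secondary endpoint (Section 5.1.2), it is summarised descriptively, and Section 7.2 plans no hypothesis test. Spelling out the numerator would not make the estimate firm, because at a long half-life most of it is extrapolated from a 24 h profile. The plan already covers that limit: the terminal-phase criterion in Section 5.4.1, and the NC code and 2/3 rule in Section 7.5.2, mean that some patients may have no value and that no summary appears if too few do.
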